**Table 2: Washout Periods (Prior to Baseline - Visit 2)** 

Product	Washout Period	During Study
Topical acne treatments (retinoids, antibiotics, benzoyl peroxide, azelaic acid, resorcinol, salicylates, α-hydroxy/glycolic acid), or other topical facial medication (antifungals, steroids, anti-inflammatories) on the treatment area, including prescription and non-prescription products	14 days	Prohibited
Systemic corticosteroids, systemic acne treatments including systemic antibiotics used for acne treatment, photosensitizing agents (thiazides, phenothiazines), spironolactone, flutamide, or immunosuppressant drugs	30 days	Prohibited
Other investigational product or device		
Systemic antibacterials	Allowed except systemic antibiotics used for acne treatment which will require a 30- day washout period	Up to 10 days allowed for indications other than acne
Facial procedures such as chemical peel, laser treatment, photodynamic therapy, acne surgery, cryodestruction or chemodestruction, x-ray therapy, intralesional steroids, dermabrasion, or depilation (except eyebrow shaping)	30 days	Prohibited [Eyebrow shaping (except for tweezing) is prohibited during the study]
Systemic retinoid (including high dose vitamin A > 10,000 units per day)	180 days	Prohibited

## **6 SUBJECT TREATMENT**

# **6.1 Investigational Products**

## 6.1.1 Description

The investigational products are:

- DFD-03 (tazarotene) Lotion 0.1%
   (60 mL bottle containing 50 ml of study product, [name] Ltd.)
- 2. Vehicle Lotion (0% tazarotene) (60 mL bottle containing 50 ml of study product, [name] Ltd.)

- 3. Tazorac (tazarotene) 0.1% Cream (60-gram tube, Allergan, Inc.)
- 4. Vehicle Cream (0% tazarotene) (60-gram tube, [name] Ltd.)

The study products will be provided by [name] Ltd., Hyderabad, India. The study products are white to off-white lotions and white to off-white creams. The ingredients of the Vehicle Lotion and Vehicle Cream are identical to DFD-03 Lotion and Tazorac Cream, respectively, except for omission of tazarotene.

## 6.1.2 Labels and Packing

Bottles (for lotions) and tubes (for creams) will be packed in individual subject kits. Each subject's study kit will consist of 1 box containing five (5) 60 ml bottles or 1 box containing three (3) 60 gram tubes of blinded and labeled study medication. For the selected site(s) enrolling subjects who can treat the chest and/or back (including shoulders), each subject's study kit will consist of 1 box containing ten (10) 60 ml bottles or 1 box containing six (6) 60 gram tubes of blinded and labeled study medication.

Labels on the bottle/tubes will be in English and in Spanish and include the protocol number, a unique kit bottle/tube number, investigational use warning, storage conditions, brief instructions for use, and sponsor name and address. In addition, there will be a place to write the subject number and subject initials. The bottle/tube label will also have a tear-off panel that includes the protocol number and unique bottle/tube number. The tear-off panel is to be affixed to the source document and filed in subject's chart.

### 6.1.3 Accountability

Documentation of receipt, study product inventory, and return shipments of the study product must be maintained at each study site. Upon receipt of the study product supplies, an inventory must be performed. It is important that site personnel count and verify that the shipment contains all the items noted in the shipment record and that they are in good condition. At study completion, all bottles/tubes of study product, used and unused, must be returned to the sponsor or designee.

In addition, an Investigational Product Dispensing Record showing dispensing to and return by subjects must be maintained at each study site. Any dispensed bottles/tubes that are not returned to the clinic must be documented on the log.

## 6.1.4 Dispensing and Return

At the Baseline Visit (Visit 2), 2 bottles or 1 tube of study product will be dispensed to each subject. At subsequent visits (Day 28 and Day 56), 1 new bottle or 1 new tube will be dispensed as required, from the same assigned treatment and used bottle/tube will be collected. Partially used bottles/tubes may be redispensed as needed.

For the site(s) selected to treat subjects with acne involvement on their chest and/or back, including shoulders, in addition to their face, 4 bottles or 2 tubes of study product will be dispensed to each subject at the Baseline Visit. At subsequent visits (Day 28 and Day 56), 3

new bottles or 2 new tubes of study product will be dispensed as required from the same treatment and used bottle/tube will be collected. Partially used bottles/tubes may be redispensed as needed.

The study product bottles/tubes will be weighed prior to being dispensed and weighed again when the bottle/tube is returned. The tear-off panel is to be affixed to the source document and filed in the subject's chart. Subject initials and subject number must be written on the bottle/tube label. Study staff will then dispense and instruct the subject on study product use. The subject will be provided with a copy of the subject instructions.

Dispensing and return of study product must be documented on the Investigational Product Dispensing Record.

In order to maintain blinding, the Investigator performing the subject assessments will not be involved with the dispensing or return of study medication. The Investigator will designate an independent third party study medication dispenser who will only dispense and collect all bottles/tubes of study product and diaries. Subjects will be instructed not to discuss or mention study product with the Investigator or study staff not designated as the independent third party dispenser.

Subjects must return the used bottles/tubes even if empty throughout the trial. At the end of the trial, all used and unused bottles/tubes must be returned to the clinic for eventual destruction by the sponsor or designee. Any dispensed bottles/tubes that are not returned to the clinic must be documented on the log.

## 6.1.5 Storage

Study product must be kept in a secure room temperature-controlled/monitored space at 20°-25°C (68°-77°F); excursions are permitted to 15°-30°C (59°-86°F).

## **6.2** Treatment Regimen

The independent third party dispenser will be involved in providing instructions to all subjects on proper application procedures and will supervise the first application on-site. The third-party dispenser will be blinded to the treatment assignment, whether the subject is receiving active vs placebo but will know the treatment group, whether the subject was randomized to the DFD-03 group or the Tazorac group.

## 6.2.1 Subjects Randomized to DFD-03 Lotion or Vehicle Lotion

Subjects will use the study product twice daily with approximately 12 hours between applications for 12 weeks starting on Day 1 during the study visit. The first application will be done at the clinic and supervised by the independent third party study medication dispenser. If the first on-site application occurs later in the afternoon (i.e., at or after 4 pm), this application will be considered the pm dose. Treatment use will begin by moistening facial skin with lukewarm tap water. Subjects will then be instructed to dispense a quarter (U.S. coin) size amount of study product into the palm of their hand and then apply over the entire face, delineated by the hairline, jawline and ears and including the nose (avoiding the areas around the eyes, mouth and nostrils), with the tip of a finger. Subjects should then rub the treated areas for 5 to 10 seconds until foamy, wait approximately 1 minute (a timer will be provided), and

then rinse thoroughly with lukewarm tap water for about 30 seconds, being careful to close eyes tightly. A washcloth should not be used on the face.

At the selected site(s), for subjects with acne on chest and/or back (including shoulders), an additional 1-2 quarter size amount of the study treatment will be similarly applied. A washcloth can be used for the chest and/or back including shoulders.

## 6.2.2 Subjects Randomized to Tazorac Cream or Vehicle Cream

Subjects will use the study product once daily in the evening. The first application will be done at the clinic supervised by the independent third party study medication dispenser and will be considered the pm dose. Subjects will then be instructed to dispense 1 gram (pea size), of study product into the palm of their hand and then apply as a thin layer over the entire face, delineated by the hairline, jaw line and ears and including the nose (avoiding the areas around the eyes, mouth and nostrils), with the tip of a finger. The applied cream on the face should be left on overnight and washed off in the morning, before applying non-medicated investigator approved sunscreen and/or moisturizer.

At the selected site(s), for subjects with acne on chest and/or back (including shoulders), an additional amount of 1-2 g of the investigational product will be similarly applied. The applied cream on the chest and/or back (including shoulders) should be left on overnight and washed off in the morning, before applying non-medicated investigator approved sunscreen and/or moisturizer.

## 6.2.3 All Subjects

The first and last dates of treatment and the number of study product applications made on these dates should be recorded on the electronic case report form (eCRF). The total number of applications (including those on the first and last days) and the number of missed applications should also be recorded by reference to the diary. By definition there are no missed applications before the first date of treatment or after the last date of treatment.

Heavy make-up used to cover-up blemishes and sunscreen should be removed before study product application using a non-medicated, gentle cleanser approved by the investigator.

Subjects will be allowed to use a non-medicated investigator-approved cleanser, face wash, sunscreen, and/or non-comedogenic moisturizer with SPF, and make-up daily on the face and chest and/back as needed. Subjects will be instructed to continue to use their investigator-approved products for the duration of the study and should avoid any changes in these consumer products.

## **6.3** Treatment and Protocol Compliance

Subjects will be provided an instruction sheet. Study staff should review the instruction sheet with the subjects to ensure protocol compliance.

At each visit, the investigator or designee will interview subjects concerning treatment compliance and ask if any doses have been missed. The study product bottles/tubes will be weighed prior to being dispensed and weighed again when the bottle/tube is returned. If the study product bottle/tube still contains study product it may be re-dispensed to the subject after

it is weighed. Additional bottles/tubes should be dispensed as needed. The investigator will also ask about compliance with protocol requirements. Protocol deviations will be recorded in the subject's chart and Protocol Deviation Form and included in the study report. A Protocol Deviation Form is not needed for missed visits, missed applications, out-of-window visits, or missing data. These items will be apparent from the missing data on the eCRF and will be identified programmatically during data analysis for purposes of reporting. The sponsor should be consulted before discontinuing subjects due to protocol deviations unless safety is a concern.

In addition, subjects will be provided a diary card for documenting the time and dates of applications. The subjects will review the diary card with the investigator or designee at each visit. The number of applied and missed applications will be recorded on the eCRF. A subject will be considered compliant if the subject applied at least 80% but no more than 120% of the expected applications during the entire evaluation period.

## 6.4 Method of Assigning Subjects to Treatment Groups

Subjects will be assigned randomly to one of the four treatment arms, DFD-03 (tazarotene) Lotion 0.1%, Tazorac (tazarotene) Cream, 0.1%, Vehicle Lotion or Vehicle Cream in a 2:2:1:1 ratio (50 subjects each to DFD-03 Lotion and Tazorac Cream, and 25 subjects each to Vehicle Lotion and Vehicle Cream). A treatment assignment schedule will be created with kit numbers randomly assigned to study products. The date and time of randomization and the bottle/tube number should be entered on the eCRF.

For the selected site(s) enrolling subjects in the 9-11 age group, subjects will be assigned randomly to one of the two treatment arms, DFD-03 (tazarotene) Lotion 0.1%, and 0.1%, Vehicle Lotion in a 1:1 ratio (4 subjects each to DFD-03 Lotion and Vehicle Lotion). A treatment assignment schedule will be created with kit numbers randomly assigned to study products, which is independent from the treatment assignment schedule created for ages 12 and older.

For the selected site(s) enrolling subjects with acne involvement on the face, chest and/or back including shoulders, subjects will be assigned randomly to treatment with either DFD-03 (tazarotene) Lotion 0.1%, Tazorac (tazarotene) Cream, 0.1%, Vehicle Lotion or Vehicle Cream in a 2:2:1:1 ratio. Since these subjects will be treating their face, chest and/or back and shoulders, the subject kit size will contain more study medication for application. A treatment assignment schedule will be created for these larger kit sizes with kit numbers randomly assigned to study products, which is independent from the treatment assignment schedules created for ages 9-11 and 12 and older.

A unique subject number will be assigned to each subject. The randomization number (kit number) will be designated as the subject number. The subject will maintain the same subject number and treatment assignment throughout the study. Subject numbers will be assigned immediately prior to dispensing study medication and will be assigned starting with the lowest available number at the study site.

The Investigator will designate an independent third party study medication dispenser who will dispense to qualified subjects, collect all bottles/tubes of study product and dispense and collect diaries.

No stratification based on age or other characteristics will be performed.

## 6.5 Blinding

## 6.5.1 Method of Blinding

This is a double-blind, active-controlled study. The primary and secondary containers and the product appearance of the DFD-03 Lotion and Vehicle Lotion will be identical and of Tazorac Cream and Vehicle Cream will be identical. All subjects, study site, CRO personnel, statisticians, and sponsor staff will be completely blinded to treatment assignment of active vs placebo but not to the treatment group of DFD group vs Tazorac group.

In order to maintain blinding, the Investigator performing the subject clinical assessments and site staff assessing AEs will not be involved with the dispensing or return of study medication. The Investigator will designate an independent third party study medication dispenser who will only dispense and collect all study medication. Subjects will be instructed not to discuss or mention study medication with the Investigator or study staff not designated as the independent third party dispenser.

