### 7. Conduct clinical assessments:

- a. IGA for the face (Table 4). IGA assessments should always be done prior to lesion counts.
- b. Count inflammatory and non-inflammatory lesions on the face and, if applicable, on chest and/or back (including shoulders) for selected site(s). These counts should be recorded separately for the face and, if applicable, chest and/or back (including shoulders) for selected site(s).
- c. Local cutaneous safety evaluation for dryness, non-lesional erythema, and peeling. The investigator should also ask the subject if any burning, stinging, or itching has occurred on the face in the last 14 days. These evaluations should be recorded separately for the face and, if applicable, chest and/or back (including shoulders) for selected site(s).
- 8. Administer the CADI questionnaire.
- 9. The independent third party study medication dispenser will perform the following procedures:
  - a) Assign a subject number using the subject kit #. Randomize subject by using the lowest available number of study kit at the study site.
  - b) Weigh and then dispense 2 bottles or 1 tube of study product (depending on the treatment assignment) to subjects. For the selected site(s) who will enroll subjects with acne on the chest and/or back, weigh and dispense 4 bottles or 2 tubes of study product. The tear-off panel is to be affixed to the source document and filed in subject's chart. Instruct subject on study product use. Review the Subject Instructions with subject. Instruct subject to not discuss study product with Investigator or other study staff.
  - c) Supervise the first application of study product at the site to ensure that it is done correctly.
  - d) Remind subject to bring all bottles or tubes of study product to next visit.
  - e) Dispense and review use of diary. Remind subject to report missed applications and/or potential AEs as well as any medication used in the diary and to bring diary to each visit.
- 10. Schedule next visit.
- 11. Complete eCRF for randomized subjects. For every screen failure subject, record the subject number, date of visit, date of consent, reason for screen failure, and study status (screen failure) in the eCRF.

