## **8.2** Recording Adverse Events

The investigator will record all AEs, regardless of relationship to study product on the AE eCRF. Standard medical terminology should be used when describing AEs. Whenever possible a diagnosis should be made and recorded on the eCRF rather than listing signs and symptoms. Intermittent AEs can be recorded once. The anatomical location of the AE must be specified when applicable. The following information should be recorded on the eCRF:

- 1. Description, including whether on treated area or not
- 2. Start date
- 3. Stop date or date of death, ongoing, or unknown
- 4. Severity of the event (see Section 8.3.1 Severity for details)
- 5. Study product use continued or not
- 6. Outcome of the event (recovered/resolved, recovered/resolved with sequelae, not recovered/not resolved, unknown, fatal)
- 7. Relationship to study product (see Section 8.3.2 Relationship to Study Product [Causality] for details)
- 8. Indication of whether the event is serious (see Section 8.3.3 Seriousness for details)
- 9. Actions taken including treatment with concomitant medication

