## 8.3.2 Relationship to Study Product (Causality)

It is the investigator's responsibility to assess the relationship between the study product and the AE. The degree of "relatedness" of the AE to the study product should be described using the following categories:

- 1. Not Related: The event is clearly due to extraneous causes (e.g., diseases, environment, etc.). Specify if known. Or, the event is most probably produced by other factors such as the subject's clinical state, therapeutic interventions, or concomitant therapy and does not follow a known response pattern to the study product.
- 2. Possibly Related: The event is temporally related to study product use but can be explained by another etiology. Information on the effect of study product withdrawal may be lacking.
- 3. Probably Related: The event is temporally related to study product use and is consistent with known effects of the study product and/or improves upon withdrawal of the study product.
- 4. Definitely Related: The event follows a reasonable temporal sequence from the time of study product administration and/or follows a known response pattern to the study product, and could not have been produced by other factors such as the subject's clinical state, therapeutic intervention, or concomitant therapy, and either occurs immediately following study product administration or improves on stopping the product, or there is a positive reaction at the application site.

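### Subjects are told not to mention the product to the people who must judge whether it caused an adverse event; the passages contradict each other and leave a narrow gap in AE capture

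*Protocol*

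**What the plan says.** Protocol 6.5.1 carries the main instruction: "Subjects will be instructed not to discuss or mention study medication with the Investigator or study staff", the only exception being the independent dispenser. Section 6.1.4 says the same of study product: "Subjects will be instructed not to discuss or mention study product with the Investigator". The dispenser repeats it at Baseline (7.10.2, item 9b): "Instruct subject to not discuss study product with Investigator or other study staff". Item 8b of 7.10.3 (Week 4) and of 7.10.4 (Week 8) repeats it again. None of these places excepts symptoms, missed applications or stopping.

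The ban reaches the people who assess adverse events, because 6.5.1 separates them from the dispenser: "site staff assessing AEs will not be involved with the dispensing or return of study medication".

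Other sections give those people tasks that need product-use information. Section 8.3.2 states: "It is the investigator's responsibility to assess the relationship between the study product and the AE". Its Probably Related category asks whether the event is "consistent with known effects of the study product and/or improves upon withdrawal of the study product". Item 5 of 8.2 requires, for each event, "Study product use continued or not". Item 6 of 7.7 has the investigator record the date of last application at early withdrawal. Section 6.3 has the investigator or a designee ask about missed doses at each visit and go through a diary of application dates and times with the subject.

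**The concern.** The ban covers any mention of the product, not only its identity. Read literally, a subject may not tell the investigator that the skin burns after each application, or that a rash cleared during a few days off treatment. Those are the facts on which 8.3.2 turns.

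Tolerability and adverse events are the primary endpoint (Protocol synopsis and section 4; SAP 3.2.1). Related TEAEs and TEAEs leading to treatment discontinuation are rows in the SAP 9.3.4.1 overview. The causality rating also decides whether a non-serious event that does not stop treatment must be followed to outcome (section 8), whether a withdrawal for an AE must be notified to the sponsor within 5 days (8.5), and whether an early discontinuer stays in the per-protocol population (11.2.3; SAP 6.5.4).

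**Working it through.** No arithmetic applies. The check sets what the investigator's side must know against the ban and against the other routes in the protocol.

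| Information needed | Required by | Under the ban | Other route |
|---|---|---|---|
| Named local reactions | 7.6; 7.10.3–7.10.5, item 2c | Not affected: need not mention the product | Examined (erythema, peeling, dryness) or asked about (stinging, burning, itching) at Visits 2–5; recorded as an AE if worse than Baseline |
| Other AEs | 7.6; section 8 | Affected if the subject would describe them through the product | Directed questioning, observation, diary |
| Missed applications | 6.3; item 1 of 7.10.3–7.10.5 | Barred | Diary; the 6.3 interview, which itself breaches the ban |
| Times of application | 8.3.2 | Barred | Diary (6.3) |
| Use continued or not | 8.2, item 5 | Barred | Partly, from missed applications in the diary |
| Date of last application | 7.7, item 6 | Barred | Diary-based treatment record (6.2.3) |
| Effect of pausing or stopping | 8.3.2 | Barred | No described field |
| Delay from application to symptom | 8.3.2 | Barred | Diary gives application times; 8.2 asks for an AE start date, not a time |
| Immediate reaction at first application | 8.3.2, Definitely Related | Seen by the dispenser | None at that visit (below) |

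**Causality.** Of the four categories in 8.3.2, three (Possibly, Probably and Definitely Related) refer to timing relative to product use, to the effect of stopping, or to both.

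**First application.** Visit 2 skin assessments come before it (7.6). The dispenser supervises it (6.2; 7.10.2, item 9c), and 6.5.1 confines that person to dispensing and collecting. No section gives the dispenser a duty to report what is seen. The next scheduled AE collection is Week 4, Day 28 ± 3, that is Day 25 to 31. The Week 4 question on stinging, burning and itching looks back to the last visit, so it covers this application, but only through the subject's recall.

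**Diary.** Section 6.3 has it reviewed with the investigator or designee. Sections 6.1.4 and 6.4 give its dispensing and collection to the dispenser. Who the designee is, and whether that person sees the diary as an AE source, is not stated. A site that takes the ban literally could leave the diary with the dispenser.

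**What the ban needs to protect.** Section 6.5.1 blinds active versus vehicle and says the site is not blinded to product group. Subjects do not know active from vehicle either. What they can reveal is formulation and regimen: lotion or cream, rinsed off or left on, twice or once daily. Saying that a symptom followed application, or cleared when use stopped, reveals none of these. The ban is therefore wider than that purpose needs.

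**The case against.** The strongest reply is that the protocol already collects most of this information. The Baseline item that contains the ban goes on, at 9e, to have the dispenser remind subjects to enter missed applications and potential AEs in the diary. Visits 3 to 5 and unscheduled visits require the diary to be reviewed for AEs. AEs are also sought by directed questioning and observation, and the main local reactions are examined or asked about at every treatment visit. All of this stands. A reader might infer that the dispenser is the only person a subject can tell, or that reactions have no route to the investigator; the diary and the questioning show otherwise.

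A reader might also infer that counts of Related TEAEs would be lowered. That is not established. Related includes Possibly Related, which accepts that withdrawal information may be absent, and SAP 9.3.4.1 counts a missing relationship as Related. Lost information on stopping may move an event between related grades without making it unrelated. Discontinuation is also recorded separately, through the withdrawal reason (7.7) and the overall tolerance grade.

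What the reply does not remove is the contradiction. The interview and diary review are not written as exceptions to the ban: a subject cannot answer the missed-dose question in 6.3 and also obey 6.5.1. Nor do these routes describe how the effect of a pause, or a reaction seen by the dispenser, reaches the assessor.

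**Conclusion.** The contradiction is real and rests on explicit text. It affects collection of primary safety data, but the gap is narrow: unprompted events that a subject would describe by reference to the product, the effect of pausing use, and immediate reactions at the supervised first application. Most named local reactions and application times should still be captured if 6.3 and 7.6 are followed.

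The size cannot be estimated. It is tempting to apply the 1% to 5% rates in section 8 for pruritus, irritation, face pain and stinging to 50 subjects per active arm (50 × 0.01 = 0.5; 50 × 0.05 = 2.5) and conclude that one or two withheld reports could remove an event from an arm. The documents do not support this: pruritus and stinging are asked about at each treatment visit, the rates are for tazarotene cream and not the rinse-off lotion, and nothing indicates how many reports would be withheld. They also give no basis for saying that losses would fall mainly in one arm, or that younger subjects would take the instruction more literally.

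The conclusion assumes that subjects and sites may follow the ban as written. The subject instruction sheet mentioned in 6.3 is not among the documents and may soften it. On this footing, the change is a worthwhile, inexpensive improvement to AE capture, not a correction on which the trial's comparison depends.

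**What to change.** Reconcile 6.1.4, 6.5.1 and 7.10.2–7.10.4 with 6.3, 7.7, 8.2 and 8.3.2:

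- Limit the ban to the product's form, appearance, method of application and frequency.
- State in the same sentence that subjects must tell the AE staff about any reaction or other problem, when it occurred in relation to use, and whether they missed or stopped applications.
- Have the dispenser pass to the AE assessor, on a short form without formulation or regimen details, any reaction seen or reported, including at the supervised first application, and the dates on which use stopped or resumed.
- Name who reviews the diary, since 6.3 and 6.1.4 can be read differently.
- Bring the subject instruction sheet into line.

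The cost is protocol and subject-instruction wording plus one hand-over form, with no new visits or staff. The downside is a slightly higher chance that a subject reveals the formulation while describing a reaction; the narrowed wording limits this.
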